An Integrated Brief Alcohol and PTSD Intervention for Veterans in Primary Care

NCT03812146

Document Date: May 6, 2021 (date of last IRB review of the protocol)

Randomized Controlled Trial of PC-TIME

Specific Aim 2 is to conduct a 2-arm pilot RCT of our adapted PC-TIME compared to a PC treatment as usual (PC-TAU) (n=60). All interventions will be completed in person. All participants will complete assessments at baseline, post-treatment, 14-week follow-up and 20-week follow-up. We will test our primary hypothesis that heavy drinking veteran PC patients receiving PC-TIME will reduce their percentage of heavy drinking days and PTSD severity compared to those receiving PC-TAU.

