C4.4. Participant Recruitment. Recruitment will use a method already shown to be effective (see B1). Patients screening positive on the PC-PTSD screen and/or AUDIT-C, which are delivered as part of standard practice nationally in VA, will be referred by their PC or PCMH providers. Research staff will facilitate the referral process by using electronic medical record data to create monthly lists of patients screening positive and then asking their providers to refer these patients to the study. Research staff will send a letter to all referred veterans introducing the study. Study staff will then contact referred patients by phone to assess their interest in participation. Interested patients will be scheduled for a baseline research appointment within their PC clinic where study eligibility will be determined, including administering the AUDIT and PCL-5. Women will be over-sampled by devoting study resources to recruit from the Women's PC Clinics. To illustrate this recruitment method, in the Web CBT study (see B1) over a 27-month period 2,057 veterans screened positive on the AUDIT-C and/or PC-PTSD within their PC clinic. Study staff was able to contact 973 of these veterans by phone and 217 were scheduled for a baseline interview. Of the 217, 162 were determined eligible to be randomized. These numbers equate to recruiting 5 eligible participants per month. Based on the success of prior studies and our anticipated recruitment pool at Buffalo, Syracuse and Binghamton, we expect to be able to enroll 3.5 eligible participants per month. This will allow us to recruit 60 participants over 17 months.

C4.5. Assessment and Randomization. Baseline assessments will be conducted in person. Trained, VA-based research staff will obtain informed consent and HIPAA authorization. An interactive program (Qualtrax) on a laptop computer will administer the questionnaires. We have used computerized assessment in several previous studies to facilitate data collection and entry and to provide the input for the computer-generated feedback sheet used within the BMI. Following completion of the computerized self-report measures, participants will be randomly assigned to treatment condition. Urn randomization will be used to ensure a balanced distribution of key patient factors across treatment groups⁷². Included in the urn randomization: 1)

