AUDIT score ≥ 15 , 2) PCL-5 ≥ 50 , 3) gender. Demographic and severity cut-points are informed by distributional data from previous study databases. We have used these variables in previous studies with success at obtaining similar groups in each treatment condition at baseline.

Following randomization participants will complete the Clinical Administered PTSD Scale (CAPS-5). While a CAPS-5 is not needed to determine study inclusion, it will serve as the primary PTSD outcome measure because it is a more sensitive measure of PTSD severity than the PCL-5 self-report. We carefully considered whether PTSD diagnosis with the CAPS-5 should be required for study inclusion and decided that using the established cut-point on the PCL-5 provided a more ecologically valid measure for a PC-based study. A 1-hour clinical interview such as the CAPS-5 could not feasibly be used in typical PCMH practice.

A post-treatment assessment (8 weeks) and two follow-up assessments (14 weeks; 20 weeks) will be conducted following baseline (Table 5). For a brief treatment like PC-TIME, we expect the largest treatment effects (for both alcohol use and PTSD) to be at post-treatment. The purpose of follow-ups are to examine if change is maintained and to assess engagement in additional treatment. Our four assessment points will allow for a more precise trajectory of change overtime. We chose 20 weeks for our final follow-up because this is the longest interval that our study timeline would allow. Follow-ups will be in person or by phone (based on participant preference) by study staff and were designed to reduce participant burden and minimize drop-out.

C4.6. Participant Payment. Participants will be paid for time spent completing assessments at a rate of approximately \$20/ hour (baseline session- \$40, post-treatment (week 8)- \$40, 14-week follow-up- \$20, 20-week follow-up- \$20, \$20 bonus for completing all study procedures) and can earn up to \$160. Reimbursement will be by check mailed to the veteran's home. Participants will not be reimbursed for intervention sessions.

C5. Measures

C5.1. Screening Measures

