Alcohol Use Disorders Identification Test (AUDIT)⁷³. This 10-item questionnaire, developed by the WHO, identifies patients whose alcohol consumption has become harmful. Questions are scored from 0-4 with a cumulative score range of 0-40. A score of 8 or higher reflects heavy use,⁷⁴ but more recent research has identified an alternative cut point of 6 or higher for females⁷⁵. The AUDIT is used to establish eligibility.

PTSD Checklist-5 (PCL-5). This 20-item self-report measure asks respondents to rate how much they have been bothered by DSM-5 PTSD symptoms in the past month on a 0 - 4 Likert-type scale⁷⁶. The PCL-5 will be administered with the extended criterion A (traumatic event) assessment. A cut point of 33 along with meeting criterion A will be required for study inclusion⁷⁷. The total score will be used to indicate PTSD severity at post-treatment and follow-up.

Mini-Mental Status Exam (MSE). This interview determines if a patient has cognitive dysfunction and should therefore not be recruited. The MSE has sections on orientation (8 items), memory (2 items), and attention (2 items). Patients who score under 18 (highest score is 26) will not be enrolled. We have used this MSE in similar studies with good success^{15, 66}.

C5.2 Outcome Measures

Alcohol Use and Alcohol-Related Problems. Alcohol use and problems will be assessed using the 30-day Timeline Follow Back Interview (TLFB)^{78, 79} and the Short Inventory of Problems (SIP)⁸⁰. Indices from the TLFB include percentage of heavy drinking days ($\geq 4/5$ drinks in one day for women/men), percentage of drinking days, average number of drinks per drinking day, and a dichotomous variable indicating whether one's past 30-day drinking pattern would be classified as excessive drinking by the CDC; (i.e., $\geq 8/15$ drinks per week for women/men)^{81, 82}. The 15-item SIP yields a total score with high internal consistency (.98) and is a valid measure of adverse alcohol consequences.

Clinician Administered PTSD Scale-5 (CAPS-5). This 30-item structured interview assesses DSM-5 symptoms of PTSD⁸³. It includes assessment of traumatic events and symptom severity ratings are based on symptom frequency and intensity. CAPS-5 will be administered by study staff at baseline and post-treatment and will be the primary measure of change in PTSD symptom severity. A 10-point decrease is considered clinically significant as is associated with meaningful improvement in quality of life for veterans with PTSD⁸⁴.

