C5.4. Secondary Outcomes

Post-intervention Treatment Engagement. With HIPAA authorization, information from participants' VA administrative data will be extracted to assess if treatment condition relates to engagement in specialty mental health and substance use visits. Number of visits attended and prescriptions of psychiatric and substance use medications between enrollment and 20 week follow-up will be extracted for each participant. Drs. [name] and [name] have expertise in this type of data extraction. In addition, participants will be asked about non-VA treatment at each assessment point using the Treatment Services Review⁸⁶.

C6 Treatment Conditions

C6.1. Experimental Condition: PC-TIME. Participants randomized to the PC-TIME condition will participate in the intervention developed in the earlier study phases (see C1.2). Sessions will be conducted in-person and will be recorded for the purpose of monitoring protocol adherence.

C6.2. Control Condition: PC-TAU. PC-TAU consists of mandatory annual screens for all patients with the

AUDIT-C and PC-PTSD. Patients who score a 4 or higher on the AUDIT-C receive a Brief Advice intervention from their PC medical provider that is built into the electronic medical record as a mandatory response to a positive screen. In addition, patients who score positive on the AUDIT-C or PC-PTSD are offered a referral to the PCMHI provider within the PC clinic. PCMHI in VA consists of licensed, independent providers (typically psychologists or clinical social workers) providing brief assessment and interventions to veterans and consultation to other members of the PC team. Patients are often treated in PC for a few sessions then referred to specialty mental health and substance abuse care, if problems persist. On average, 4 PCMHI sessions are provided to PTSD patients typically focused on assessment, psycho-education, and supportive counseling ¹⁰. VA PC patients often decline referrals for alcohol use following the receipt of brief advice. There will be variability in the amount of provider contact PC-TAU participants receive, therefore we will closely measure the number and type of PC-TAU contacts and consider it as a covariate in our analyses.

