Preliminary analyses will examine distributional properties of variables and correlations among DVs. For highly collinear DVs, we will consider data reduction methods such as principal components analyses to create composite scores (this reduces the total number of tests conducted). Because we use in-person (or phone) assessments, missing data for specific questions and measures are expected to be minimal (see D3 for missing data). We will conduct multilevel growth curve modeling permitting us to estimate the between- and within-person change trajectories over time (Time: baseline, week 8 [post-tx], week 14 [F/U 1], week 20 [F/U 2]) and intervention impact (Group: PC-TIME, PC-TAU) on a given outcome variable. Time will serve as the Level 1 predictor and treatment condition on Level 2 to yield the following fixed effect equation: DV (percent of heavy drinking days or PTSD severity) = $\beta_{00} + \beta_{10}\text{Time}_{ti} + \beta_{01}\text{Treatment}_i + \beta_{11}\text{Time}_{ti} * \text{Treatment}_i + e_{ti}$. Raw data will be plotted and model fit indices will be used to determine whether change is optimally modeled linearly or

curvilinearly. Growth modeling is a powerful and flexible method well-suited for handling longitudinal data particularly in cases with missing data, nonlinear trajectories, and time-varying covariates.

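### No masking of the assessor is described for the interviewer-rated primary PTSD measure, and the baseline CAPS-5 is taken after randomization

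*Combined protocol and SAP*

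**What the plan says.** C5.2 (Outcome Measures) names both the instrument and who gives it: "CAPS-5 will be administered by study staff at baseline and post-treatment and will be the primary measure of change in PTSD symptom severity". Week 8 is therefore the only post-baseline CAPS-5 value. C5.2 also says that severity ratings rest on symptom frequency and intensity.

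C4.5 (Assessment and Randomization) gives the order of the baseline assessment. First, "Following completion of the computerized self-report measures, participants will be randomly assigned to treatment condition". Then, "Following randomization participants will complete the Clinical Administered PTSD Scale (CAPS-5". On later contacts it says "Follow-ups will be in person or by phone (based on participant preference) by study staff".

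The alcohol outcome is also an interview: "Alcohol use and problems will be assessed using the 30-day Timeline Follow Back Interview (TLFB". C5.2 does not name who gives it, and C4.5 does not say whether the baseline TLFB comes before or after allocation.

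C5.4 adds that "participants will be asked about non-VA treatment at each assessment point using the Treatment Services Review". C6.1 and C6.2 set in-person, recorded PC-TIME sessions against usual care that is deliberately left unmanualized.

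The efficacy hypothesis, in the opening section, is that "heavy drinking veteran PC patients receiving PC-TIME will reduce their percentage of heavy drinking days and PTSD severity compared to those receiving PC-TAU". D1 tests the primary variables at post-treatment with a two-sided alpha of 0.05.

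**The concern.** The CAPS-5 score depends partly on the interviewer's judgment. An interviewer who knows the arm and expects PC-TIME to work can, without intending to, score PC-TIME participants lower at week 8. The baseline interview is exposed too, because it takes place after allocation.

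This kind of error is systematic. The growth model, covariate adjustment and FIML in D1 and D3 deal with trajectories, imbalance and missing values; none of them can separate a treatment effect from a rater effect that runs along with treatment. The bias would enter the week-8 between-arm comparison. It would also enter the effect size estimates that the Statistical Analysis Plan intends to use, with other evidence, in sizing the next trial.

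**Working it through.** **Step 1. What the text establishes and what it leaves open**

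| Question | Where | Answer in the text |
|---|---|---|
| Who gives the CAPS-5? | C5.2 | Study staff |
| When? | C5.2 | Baseline and week 8 only |
| Baseline CAPS-5 before or after allocation? | C4.5 | After |
| Who randomizes, and who learns the arm? | C4.5 | Not stated |
| Are assessors separate from allocation or therapy staff? | No section | Not stated |
| Is masking or independent re-rating described? | No section | No; the only recording described is of PC-TIME sessions, for adherence (C6.1) |
| Who gives the TLFB, and when at baseline? | C4.5, C5.2 | Not stated for baseline; study staff conduct follow-ups |
| Could an assessment reveal the arm? | C5.4, C6.2 | Plausibly: treatment use is asked at each assessment and usual-care contacts are closely measured |

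The timing of the baseline CAPS-5 is documented. The absence of any described masking is also plain from the text. That the interviewer knows the arm is an inference from the order of events.

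**Step 2. The plan's own figure**

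C4.2 recruits 60 to retain 51 at 85%: 60 × 0.85 = 51, and 51 / 0.85 = 60. This reproduces. The documents give no power, effect size or SD for the CAPS-5, so there is no stated operating characteristic to check.

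**Step 3. Illustration of what a rater shift would do**

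Inputs from the documents: 51 analysed (C4.2) and two-sided alpha 0.05 (D1). Assumptions: 1:1 allocation, so 25.5 per arm; no true effect; a rater shift of *b* SD in favour of PC-TIME; a normal approximation to a two-group comparison at week 8.

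SE = √(2 / 25.5) = 0.280 SD

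Rejection rate = [1 − Φ(1.96 − b/SE)] + Φ(−1.96 − b/SE)

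| Assumed b (SD) | b/SE | Upper tail | Lower tail | Total |
|---|---|---|---|---|
| 0 | 0 | 0.025 | 0.025 | 5.0% |
| 0.1 | 0.357 | 0.0545 | 0.0103 | 6.5% |
| 0.2 | 0.714 | 0.1064 | 0.0037 | 11.0% |
| 0.3 | 1.071 | 0.1871 | 0.0012 | 18.8% |

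**Step 4. Sensitivity to the assumptions**

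- *Sample size.* The 51 is a 20-week figure, so more may be available at week 8. With all 60, SE = √(2/30) = 0.258, and the same shifts give 6.7%, 12.1% and 21.3%.
- *Baseline adjustment.* With an assumed baseline correlation of 0.6, SE = √(2 × (1 − 0.36) / 25.5) = 0.224, giving 7.3%, 14.5% and 26.8%. Greater precision makes a fixed bias easier to mistake for an effect.
- *CAPS-5 points.* For an assumed SD of 8 to 14, a 2-point shift gives 14.5% down to 8.0%, and a 3-point shift 26.8% down to 11.9%. For scale, C5.2 treats a 10-point decrease as clinically significant.

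**The case against.** The strongest reply is that the plan is silent on masking, and silence does not show that raters are unmasked. Randomization is described in the passive, nobody is named as learning the arm, and the baseline and week-8 interviewers need not be the same person. Some numbered sections (C5.3, D2) and Table 5 are not in the text available. This stands. A reader might infer that the workflow is documented as exposing raters to the allocation; the documents do not support that. They support only that no safeguard is described and that the sequence makes exposure likely.

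A reader might also extend the point to the TLFB with equal force. That is not supported either. The TLFB counts drinks that the participant reports, its administrator is not named in C5.2, and participant reporting may matter more there than rater judgment.

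A third reply is that the trial's stated primary goal is feasibility and acceptability, that pilot effect sizes are to be weighed alongside larger trials, and that the self-report PCL-5 offers a rater-independent check. Each is true and limits the consequence. But the plan still states an efficacy hypothesis, tests it at 0.05, and calls the CAPS-5 its primary PTSD outcome because it is more sensitive than the PCL-5. The PCL-5 also remains open to participant expectation.

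Finally, one might think that moving every week-8 CAPS-5 to a remote rater by phone is already permitted. C4.5 offers phone for follow-ups at the participant's preference, and it lists the week-8 post-treatment assessment separately from the two follow-ups. D1 refers to assessments generally ("Because we use in-person (or phone) assessments"), but in a sentence about missing items. Compulsory phone rating at week 8 would also change mode from the in-person baseline, so it should be no more than an option.

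**Conclusion.** The concern holds in this form: no masking of the CAPS-5 assessor is described, the baseline CAPS-5 follows randomization, and the week-8 CAPS-5 is rated by study staff with no stated separation from allocation or therapy. Followed as written, this leaves the CAPS-5 comparison and the planning effect size open to rater bias that analysis cannot repair. It should be changed, although it does not undermine the feasibility aims.

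The size of any bias is unknown. The rise from 5% to about 6.5%, 11% or 19% shows only how a shift of 0.1, 0.2 or 0.3 SD would behave with about 51 analysed. The shifts, the 1:1 split and the simple week-8 comparison are assumptions, and that comparison is not the planned growth model. The figures should not be read as an estimate of error in this trial.

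**What to change.** Amend C4.5 and C5.2 as follows.

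1. Complete the baseline CAPS-5 and TLFB before randomization. This cures the documented ordering fault but does not protect week 8.
2. Have the week-8 CAPS-5, and where feasible the post-baseline TLFB, done by an existing trained staff member who did not run that participant's randomization visit, does not deliver PC-TIME and cannot see the assignment. C4.3 describes three sites, so a rater at another site working by phone is a possible option; if it is used, state that phone is allowed for the week-8 CAPS-5 and apply it alike in both arms.
3. Script a request that participants not mention their treatment. Ask the Treatment Services Review and treatment-contact questions after the CAPS-5 and TLFB. Record whether the rater became unmasked, and when.
4. In D1, report the PCL-5 as a rater-independent sensitivity analysis, noting that it does not remove participant expectation.

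If assessors are in fact already masked and separate, saying so settles most of item 2.

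Cost: some scheduling among existing staff, one extra data field, and possibly some phone interviews in both arms. The documents do not show how many staff at each site are trained in the CAPS-5, so the sponsor should confirm that swaps are workable. In a pilot, the recorded unmasking rate would itself be useful feasibility information for the larger trial.

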C4.1. Description of the Sample. Veterans enrolled in PC within VA facilities in Syracuse and Binghamton, NY will be screened for eligibility. The open trial will not include Buffalo participants due to budgetary limitations, (i.e., unable to staff Buffalo in year 1 to recruit, assess and treat patients). Inclusion criteria: Patients who score a) 8-19 for men, 6-19 for women on the AUDIT and have past month drinking (i.e., have not quit drinking over the last month); and b) score ≥ 33 on the PTSD Checklist-5 (PCL-5) and report a traumatic event on the Criterion A screener. Exclusion criteria: Patients will be excluded if they 1) score a 20 or higher on the AUDIT as previous research has demonstrated the BMIs are less effective with very severe drinkers (see C2.2.a) and/or 2) demonstrate symptoms that would not allow them to actively engage in the intervention such as gross cognitive impairment and/or current symptoms of mania or psychosis. Patients will also be excluded if they have more pressing concerns that need to be addressed first: 3) in need of detox services, or 4) suicide attempt in the last two months or current intent to commit suicide. Patients with recent suicide attempts or intent may be enrolled following receipt of suicide prevention services. We will also exclude patients that 5) are already receiving psychotherapy for heavy drinking or PTSD outside of PC, 6) started or changed the dose of a psychotropic medication for heavy drinking or PTSD in the last two months that was prescribed outside of VA PC, and 7) voice a preference to be directly referred to VA specialty care for heavy drinking or PTSD. These final 3 exclusions are to allow the study to isolate the effects of the intervention and to ensure that patient preference for services is honored. In RCTs for Veterans with PTSD^{63, 64}, the effect of a psychotropic medication is typically considered to be stable after 2 months; therefore it should not confound the effect of the intervention.

C4.2. Sample Size. We will recruit a total of 60 patients to retain a minimum sample size of 51 (85% retention) at 20-week follow-up. This retention rate was observed in our previous work (See A2.1, B1).

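### The VA treatment-engagement outcome has no described pre-enrollment measure, so earlier prescriptions and some continuing visits add avoidable noise to the comparison of arms

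*Combined protocol and SAP*

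**What the plan says.** Section C5.4 (Post-intervention Treatment Engagement) draws VA administrative data "to assess if treatment condition relates to engagement in specialty mental health and substance use visits". The fields and dates are: "Number of visits attended and prescriptions of psychiatric and substance use medications between enrollment and 20 week follow-up will be extracted for each participant". Care outside VA is handled differently: "participants will be asked about non-VA treatment at each assessment point using the Treatment Services Review". Baseline is one of the four assessment points, so non-VA care has a baseline measure.

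Two exclusions in C4.1 limit what patients bring with them. Exclusion 5 removes those who "are already receiving psychotherapy for heavy drinking or PTSD outside of PC". Exclusion 6 treats a new start and a dose change alike, removing anyone who "changed the dose of a psychotropic medication for heavy drinking or PTSD in the last two months that was prescribed outside of VA PC". Medication that has been stable for longer than that, and any medication prescribed within VA primary care, is compatible with entry.

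Prior service use does not appear among the balancing or adjustment variables:

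- The urn factors in C4.5 are "AUDIT score ≥ 15 , 2) PCL-5 ≥ 50 , 3) gender".
- The baseline comparison in D1 names sociodemographic and alcohol variables.
- The covariate raised in C6.2 is PC-TAU contact during the trial, which is measured after randomization.

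**The concern.** C4.5 gives one purpose of the follow-ups as assessing whether patients take up further treatment. Further treatment can be recognised only against what the patient was already receiving, and for VA care, the main source, the visible text gives no such reference. A refill in week 3 of a long-standing prescription and a first prescription in week 3 yield the same record. So do a routine visit to an existing specialty prescriber and a first specialty visit.

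What is at stake is precision. The opening of the Statistical Analysis Plan says that between-condition effect sizes with 95% confidence intervals will help to size a later trial. If this outcome carries large stable differences between patients that predate the study, its standardized effect will be smaller and its interval wider than they need be. In a sample of 60, an accidental imbalance in prior users could also not be examined or adjusted for.

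**Working it through.** **The plan's own figure.** C4.2 recruits 60 and expects 85% retention: 60 × 0.85 = 51, as stated. The plan gives no rate, effect size or power for engagement, so everything below is for scale. It assumes 30 per arm, since the allocation ratio is not stated.

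**Step 1: what can carry over.** Setting C4.1 beside C5.4:

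| Type of VA care | Allowed at entry? | Falls in the enrollment-to-week-20 window? |
|---|---|---|
| Stable psychotropic medication | Yes | Yes, as refills |
| Medication recently started in VA primary care | Yes | Yes, as refills |
| Psychotherapy for heavy drinking or PTSD outside primary care | No (exclusion 5) | Not as carry-over |
| Specialty prescriber visits on stable medication; care for other conditions | Not excluded as such | Yes |

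Prescriptions are therefore the main route, and visits a lesser one.

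**Step 2: effect on a difference in counts.** Write a participant's count as Y = B + N, where B is continuing use and N is new use. Randomization gives B the same distribution in both arms in expectation, so E(Y₁) − E(Y₀) = E(N₁) − E(N₀). The absolute mean difference is not shrunk. If B and N are independent, Var(Y) = Var(B) + Var(N), so the standard error rises and the standardized difference falls.

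**Step 3: what a pre-period value would recover.** With correlation r between the pre-period and trial-period values, adjustment leaves residual variance of about 1 − r². This is exact for a linear model and only a guide for skewed counts. The documents give no value of r, so a range is shown:

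| Assumed r | 1 − r² | Variance removed | Standard error multiplied by √(1 − r²) | 60 patients act like 60/(1 − r²) |
|---|---|---|---|---|
| 0.3 | 0.91 | 9% | 0.95 | 66 |
| 0.5 | 0.75 | 25% | 0.87 | 80 |
| 0.7 | 0.51 | 49% | 0.71 | 118 |

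**Step 4: chance imbalance in prior users.** Let p be the share entering on a continuing prescription (assumed). The standard error of the between-arm difference in that share is √(2p(1 − p)/30). The chance of a gap of 6 or more patients between two arms of 30 comes from the exact binomial distribution.

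| Assumed p | Standard error | Chance of a gap of 6 or more |
|---|---|---|
| 0.2 | 0.103 | 7.5% |
| 0.4 | 0.126 | 14.7% |
| 0.6 | 0.126 | 14.7% |

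Such gaps are already reflected in an unadjusted standard error and do not inflate type I error. Without a pre-period measure, however, they can be neither seen nor adjusted for.

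**The case against.** The strongest reply is that total use after enrollment is a valid randomized comparison, that exclusions 5 to 7 were written to isolate the intervention's effect, and that this is a secondary outcome in a pilot whose stated primary goal is feasibility and acceptability. All of that stands. It limits the point to precision and interpretation, and it makes visits a smaller matter than prescriptions.

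A reader might go further in three ways that the documents do not support:

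- **That carry-over biases the comparison between arms.** It does not, because prior use is balanced in expectation.
- **That it dilutes the effect by a calculable amount.** If a share q already hold a prescription, a 20-point difference in new starts would appear as (1 − q) × 20 points in a yes/no measure of any prescription: 14, 10 and 6 points at q = 0.3, 0.5 and 0.7. The plan never defines that yes/no measure, q is not in the documents, and the formula assumes that a continuing user can never register a new start. For counts, step 2 shows that the absolute difference is unchanged.
- **That the plan scores refills as new engagement.** C5.4 says what is extracted, not how the engagement variable is built.

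It can also be said that a baseline item may exist out of view. Table 5 is not shown, and the numbering passes from C5.2 to C5.4 and from D1 to D3. That caveat stands.

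**Conclusion.** On the visible text, VA visits and prescriptions have no pre-enrollment measure, and the entry criteria let existing prescriptions, and to a lesser extent existing visits, into the outcome window. The consequence is added variance, smaller standardized effects and unadjusted chance imbalance, with no systematic bias. The variance that could be recovered is about 25% at r = 0.5 and 49% at r = 0.7, and only 9% at r = 0.3. These figures rest on assumed correlations, equal allocation and a linear model. No main conclusion of the trial depends on this outcome, so it is a minor improvement, worth making because it is cheap.

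**What to change.** In C5.4, extract the same VA fields for the 20 weeks before enrollment, matching the length of the outcome window. Keep the planned visit and prescription outcomes, and state in the analysis plan how each is built and that each is adjusted for the participant's own pre-period value. As a supportive analysis, split prescriptions into new (absent in the pre-period) and continuing.

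Replacing the outcome with new items only is not advised. It would discard intensified care in a clinic the patient already attends, and it would make the primary definition depend on the chosen look-back length. Starting the window at week 8 would not help either, since continuing prescriptions are refilled in any window.

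The cost is a wider date range in an extraction already planned, with no added patient contact, and a check that the HIPAA authorization covers the look-back. If Table 5 or a section not visible here already provides a pre-enrollment measure, a cross-reference in C5.4 and the adjustment rule would be enough.
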